9.5 Monitoring

Accrual reports will be created and distributed to the protocol team periodically (e.g., once a month) to ensure that the total target number of evaluable participants is enrolled. The report will include information such as screening, accrual, and retention.

The first Tuberculosis Transformative Science Group (TB TSG) Study Monitoring Committee (SMC) review took place 6 months after the study opening, and feasibility of this study was reviewed.

At the second SMC review, the TB TSG SMC reviewed the SDs of the EBA₀₋₇ (CFU) among participants in Group 1 to evaluate if the estimates of SDs used for the sample size calculations were reasonable (i.e., the SD of the EBA₀₋₇ (CFU) from Group 1 varies between 0.06 and 0.12). If the SD from each cohort in Group 1 was larger than expected, the sample size could have been increased up to 22 per cohort, to improve the precision of 95% CIs around mean EBA₀₋₇ (CFU) for Group 1 cohorts. With the increased sample size of 22, a half-width will be reduced to less than or equal to 0.053 with SDs between 0.060 and 0.120. However, the SMC determined the sample size increase from 16 to 22 in Group 1 cohorts was not necessary.

During the study, the safety and tolerability of the study medication will be monitored by means of adverse event reports (AER) and toxicity reports presenting laboratory and clinical data. The report will be stratified by group, and within Group 1, by dose. It is required that these data be entered into the database within two business days of the time at which the results of the laboratory tests or clinical examinations become available. The study team will discuss these reports on regularly scheduled conference calls or by e-mail and any concerns will be presented to the TB TSG SMC. The TB TSG SMC will also review the DAIDS Safety Monitoring Report every 3 months.

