1.2 Primary Objectives

- 1.2.1 Estimate the 7-day EBA, based on CFU counts, of INH among participants infected with TB with *inhA* mutations taking one of three doses of INH (5, 10, or 15 mg/kg daily), and participants infected with DS-TB taking standard-dose INH (5 mg/kg daily).
- 1.2.2 Estimate the 7-day EBA, based on TTD, of INH among participants infected with TB with *inhA* mutations taking one of three doses of INH (5, 10, or 15 mg/kg), **participants infected with TB with *katG* mutations taking 15 or 20 mg/kg daily**, and participants infected with DS-TB taking standard-dose INH (5 mg/kg daily).
- 1.2.3 Determine the association between the area under the curve (AUC)/MIC of INH and the EBA of INH among participants with smear-positive pulmonary TB.
- 1.2.4 Describe the safety and tolerability of doses of 5, 10, and 15 mg/kg of INH administered daily among participants with sputum smear-positive pulmonary TB.

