3.0 STUDY DESIGN

This is a two-stage, two-step, phase IIa, open-label, randomized clinical trial among adult participants with sputum smear positive pulmonary TB evaluating the EBA of three different doses of INH among participants infected with *M. tuberculosis* with *inhA* mutations (Group 1). In addition, the EBA of INH among participants with *M. tuberculosis* with no genotypic evidence of INH resistance (Group 2) will be determined. Among participants infected with an *M. tuberculosis* strain with *katG* mutations (Group 3), **the EBA of INH at a dose of 15 or 20 mg/kg will be determined. These doses are selected because doses of up to 15-20 mg/kg appear to be safe (in other studies, as well as in the 15 mg/kg dosing cohort in Group 1 in the current trial) and the safety of doses higher than 20 mg/kg has not been established. In addition, upon preliminary assessment of the EBA data in the *inhA* arms, INH demonstrated activity, and this activity appeared to be dose-related.**

No study drug is administered under Step 1. Data collected in Step 1: (a) determine eligibility to Step 2, and (b) allow characterization of INH MICs in three groups (secondary objective). Groups 1, 2, and 3 consist of participants infected with TB with *inhA* mutations, with DS-TB and with TB with *katG* resistance-conferring mutations, respectively.

The study's primary objectives are addressed via Step 2 evaluations. Participants enrolling to Step 2 receive the study drug, INH, which will be given with vitamin B6 ≥ 25 mg daily, by mouth. During both stages, participants in Group 1 who meet Step 2 entry criteria will be randomized to receive 5, 10, or 15 mg/kg of INH daily for 7 days. During Stage 2, participants in Group 2 who meet Step 2 entry criteria will receive 5 mg/kg of INH daily for 7 days. **During Stage 2, participants in Group 3 who meet Step 2 entry criteria will be randomized 1:1 to receive 15 or 20 mg/kg of INH daily for 7 days.** After completion of 7 days of INH alone, participants will be referred to begin standard anti-TB chemotherapy according to South African TB Control Programme Guidelines.

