5.1 Regimens, Administration, and Duration

Stage 1Step 1:

Group 1: Participants in Group 1 who do not meet Step 2 entry criteria but are enrolled for determination of MIC only will not receive study drug.

Groups 2 and 3: In Stage 1, participants infected with *M. tuberculosis* with neither *katG* nor *inhA* mutations (Group 2) and those infected with *M. tuberculosis* with a *katG* mutation with or without an *inhA* mutation (Group 3) will not receive study drugs.

Step 2:

Group 1 (n=15): Participants infected with *M. tuberculosis* with an isolated *inhA* mutation will be randomized 1:1:1 to receive the following treatments for 7 days:

5 mg cohort	INH 5 mg/kg by mouth once daily on Days 1-7 plus vitamin B6 \geq 25 mg daily
10 mg cohort	INH 10 mg/kg by mouth once daily on Days 1-7 plus vitamin B6 \geq 25 mg daily
15 mg cohort	INH 15 mg/kg by mouth once daily on Days 1-7 plus vitamin B6 \geq 25 mg daily

Stage 2Step 1:

Participants who do not meet Step 2 entry criteria but are enrolled only for determination of MIC will not receive study drug.

Step 2:

Group 1 (n=33): Participants infected with *M. tuberculosis* with an isolated *inhA* mutation will be randomized 1:1:1 to receive the following treatments for 7 days:

5 mg cohort	INH 5 mg/kg by mouth once daily on Days 1-7 plus vitamin B6 \geq 25 mg daily
10 mg cohort	INH 10 mg/kg by mouth once daily on Days 1-7 plus vitamin B6 \geq 25 mg daily
15 mg cohort	INH 15 mg/kg by mouth once daily on Days 1-7 plus vitamin B6 \geq 25 mg daily

Group 2 (n=16): Participants infected with *M. tuberculosis* with neither *katG* nor *inhA* mutations who meet the Step 2 entry criteria will receive the following treatment for 7 days:

Control	INH 5 mg/kg by mouth once daily on Days 1-7 plus vitamin B6 ≥25 mg daily
---------	--

Group 3 (n=20): Participants infected with *M. tuberculosis* with a *katG* mutation, with or without an *inhA* mutation, who meet the Step 2 entry criteria will receive the following treatment for 7 days:

katG 15 mg cohort	INH 15 mg/kg by mouth once daily on Days 1-7 plus vitamin B6 ≥25 mg daily
katG 20 mg cohort	INH 20 mg/kg by mouth once daily on Days 1-7 plus vitamin B6 ≥25 mg daily

INH is available in 100 mg tablets. INH will be administered orally daily in the morning on an empty stomach. Doses of INH will be given according to the weight bands outlined below:

Dose cohort	Weight	Dose
5 mg/kg	≥40 kg and ≤70 kg	300 mg
5 mg/kg	>70 kg and ≤90 kg	400 mg
10 mg/kg	≥40 kg and ≤55 kg	500 mg

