7.0 CLINICAL MANAGEMENT ISSUES

7.1 Toxicity

Only toxicities related to study medications will be considered in the toxicity management section. The grading system for drug toxicities is located in the DAIDS AE Grading Table, Version 1.0, December 2004 (Clarification, August 2009), located at the DAIDS RSC web site: <http://rsc.tech-res.com/clinical-research-sites/safety-reporting/daids-grading-tables>.

7.1.1 Grade 1

Study participants who develop a Grade 1 AE or toxicity may continue study medications at the discretion of the site investigator.

If participants choose to discontinue study drug, the A5312 Clinical Management Committee ([contact]) should be notified within 48 hours. The site should complete the premature discontinuation evaluations, as per [section 6.1.2](#), within 7 days after stopping study medications.

7.1.2 Grade 2

Participants who develop a Grade 2 AE or toxicity may continue study drugs, at the discretion of the site investigator, and will be followed carefully.

If participants choose to discontinue study drug, the A5312 Clinical Management Committee should be notified within 48 hours. The site should complete the premature discontinuation evaluations, as per [section 6.1.2](#), within 7 days after stopping study medications.

Grade 2 clinical or laboratory abnormalities that are deemed likely related to study drug will be followed to stabilization or resolution to Grade ≤ 1 . Evaluations and the frequency of follow-up visits are at the discretion of the site investigator. The A5312 Clinical Management Committee should be notified of any requirements for continuing follow-up of toxicities beyond 7 days after stopping study medications.

7.1.3 Grade 3

Unless the site investigator has compelling evidence that the Grade 3 AE or toxicity is not related to the study drug, the participant must permanently discontinue the study drug. The A5312 Clinical Management Committee should be notified within 48 hours. The site should complete the premature discontinuation evaluations, as per [section 6.1.2](#), within 7 days after stopping study medications.

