9.2 Endpoints

9.2.1 Primary Endpoints

- 9.2.1.1 Daily decline in \log_{10} CFU per mL sputum from baseline to Day 7 of study treatment, defined as EBA_{0-7} (CFU) = [baseline \log_{10} CFU per mL (mean of the pre-entry visit and entry visit sputum colony counts) – Day 7 \log_{10} CFU per mL]/7 (**Groups 1 and 2**)
- 9.2.1.2 Daily decline in TTD from baseline to Day 7 of study treatment, defined as EBA_{0-7} (TTD) = [baseline TTD (mean of the pre-entry visit and entry visit TTDs) – Day 7 TTD]/7 (**all groups**).
- 9.2.1.3 Daily \log_{10} CFU per mL sputum and TTD from baseline to Day 7 of study treatment; area under the time-concentration curve (AUC) for INH; MIC of *M. tuberculosis* isolates against INH (**Group 1 for CFU and TTD and Group 3 for TTD only**)
- 9.2.1.4 Grade 2 or higher drug-related adverse clinical or laboratory events (**all groups**)

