9.6 Analyses

9.6.1 Analyses of Primary Endpoints

9.6.1.1 Descriptive statistics of EBA₀₋₇ (CFU) for each of the cohorts in Groups 1 and 2 will be reported in a table. Box plots and a plot with four CIs will be created.

9.6.1.2 Descriptive statistics of EBA₀₋₇ (TTD) for each of the cohorts will be reported in a table. Box plots and a plot with six CIs will be created.

9.6.1.3 The relationship between the AUC/MIC and the EBA will be evaluated with linear or nonlinear models, adjusting for other covariates, such as baseline log₁₀ CFU per mL. PK/PD modeling will be performed to evaluate the relationship between drug concentrations and rate or magnitude of bacterial decline. The distributions of PK/PD parameters will be examined first and appropriate transformations will be applied if necessary.

9.6.1.4 Grade 2 or higher AEs will be reported in a tabular form by **cohorts**.

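### In-study safety reports are split by dose only in Group 1, so Group 3's randomized 15 and 20 mg/kg arms are merged

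*Protocol*

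**What the plan says.** Protocol 9.5 (Monitoring) says that safety will be followed during the study through adverse event and toxicity reports. The team discusses these and takes any concerns to the study monitoring committee (SMC). On layout it says: "The report will be stratified by group, and within Group 1, by dose".

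Group 3 has two doses under Version 3.0. Protocol 3.0 (Study Design) says these participants will be "randomized 1:1 to receive 15 or 20 mg/kg of INH daily for 7 days", and Protocol 5.1 lists a *katG* cohort receiving "INH 20 mg/kg by mouth once daily on Days 1-7". Protocol 9.4 plans 10 participants in each arm.

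The final safety analysis is set out differently. Endpoint 9.2.1.4, "Grade 2 or higher drug-related adverse clinical or laboratory events", applies to all groups. Protocol 9.6.1.4 says "Grade 2 or higher AEs will be reported in a tabular form by" cohort, which separates the two Group 3 doses.

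The safety objective, Protocol 1.2.4, repeated as SAP 2.4 item 4, reads "Describe the safety and tolerability of doses of 5, 10, and 15 mg/kg of INH administered daily" and does not mention 20 mg/kg.

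**The concern.** The 9.5 rule fits a design in which only Group 1 has more than one dose. Group 3 now has two randomized doses, and it is the only multi-dose group whose doses the reports would merge. Neither the clarification memos shown nor the SAP changes this, and no reason for merging is given.

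The merged stratum contains the dose about which the trial itself knows least. Its own safety experience, summarized in Protocol 2.1 and 3.0, comes from the *inhA* arms, which stop at 15 mg/kg. If the reports show pooled rates, events confined to 20 mg/kg would appear at about half their true rate. A report with no events would look more reassuring about 20 mg/kg than the data at that dose allow.

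The report matters most for Grade 2 events. Under Protocol 7.1 a participant with a Grade 2 event may continue at the investigator's discretion, so a cluster of such events at one dose triggers no individual stopping rule. The primary safety endpoint starts at Grade 2.

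**Working it through.** **Strata against cohorts.** The plan gives no figure to reproduce here, so the first check is a count.

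| Group | Step 2 dose cohorts | Strata under 9.5 | Strata if Group 3 is split |
|---|---|---|---|
| 1 (*inhA*) | 3 (5, 10, 15 mg/kg) | 3 | 3 |
| 2 (drug-sensitive) | 1 (5 mg/kg) | 1 | 1 |
| 3 (*katG*) | 2 (15, 20 mg/kg) | 1 | 2 |
| Total | 6 | 5 | 6 |

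Other statistical sections already work with six cohorts. Protocol 9.3 covers the Group 3 randomization, 9.6.1.2 plots six confidence intervals, and 9.6.1.4 tabulates by cohort.

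**Size of the dose difference.** From the weight bands in Protocol 5.1, a 60 kg participant takes 900 mg in the 15 mg/kg arm and 1200 mg in the 20 mg/kg arm: 1200/900 = 1.33.

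**No events seen.** The exact two-sided 95% upper limit with 0 events in n is 1 − 0.025^(1/n).

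- n = 10 (20 mg/kg alone): 1 − 0.025^(1/10) = 30.8%.
- n = 20 (pooled): 1 − 0.025^(1/20) = 16.8%.

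This comparison assumes no event rate.

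**Three events, all at 20 mg/kg.** This count is only an illustration, because the documents give no event rate for 7 days at this dose. Intervals are exact (Clopper-Pearson).

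- Shown by dose: 3/10 = 30% (95% CI 7% to 65%) at 20 mg/kg, and 0/10 at 15 mg/kg.
- Shown pooled: 3/20 = 15% (95% CI 3% to 38%).

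**What a split could show.** For 3/10 against 0/10, the chance that all three events fall in one named arm is C(10,3)/C(20,3) = 120/1140 = 0.105. Doubling this gives the two-sided Fisher p = 0.21. The split is descriptive and does not test a difference between doses.

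**Other denominators.** Ten per arm counts evaluable participants, and those who stop before the Day 7 sample are replaced. If all three participants with events were replaced in their own arm, the figures would be 3/13 = 23% by dose and 3/23 = 13% pooled. Reports are also read during accrual. With 5 treated per arm and no events, the limits are 1 − 0.025^(1/5) = 52.2% by dose and 30.8% pooled. In each case the pooled figure is clearly lower.

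**The case against.** The strongest reply is that the effect depends on a layout the protocol does not give. Section 9.5 does not say whether these reports show percentages, counts or participant listings, and it does not forbid a dose split in Group 3. That is correct: the halving of rates applies only to pooled rates. It does not remove the point, because a stated stratification that leaves out the newest dose is a poor thing to rely on.

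The second reply is that other safeguards cover the gap. Treatment is open-label and dosing is observed in hospital, so the team can find the dose behind any event. For Grade 3 events not clearly unrelated to the drug, "the participant must permanently discontinue the study drug", and any Grade 4 toxicity leads to discontinuation. Also, "The TB TSG SMC will also review the DAIDS Safety Monitoring Report every 3 months". No rule in Protocol 7.1 or 8.1 is triggered by a rate in these reports. These points stand and keep the concern small. They do not close it: the individual rules do not act on Grade 2 events, the layout of the quarterly report is not described, and the by-cohort final table comes after dosing has ended.

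Third, the risk at 20 mg/kg is modest. Protocol 2.1 states that doses up to 20 mg/kg have been well tolerated in other studies, and exposure here is 7 days with vitamin B6. This also stands. It lowers the chance that a dose signal exists, but it is not a reason to hide one.

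Finally, that the sentence was overlooked when Group 3 dosing was added is an inference from the surrounding text. The mismatch with the current design does not depend on that inference.

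**Conclusion.** The concern holds and is minor. As written, the in-study safety reports have five strata for six dose cohorts, and the merged pair contains the trial's highest and newest dose. With no events in the planned numbers, a reader of the pooled line could take 16.8% as the upper limit where the data at 20 mg/kg support only 30.8%. This assumes 10 treated participants per arm and a report read at the level of its strata. Nothing here affects the final safety table, the EBA estimates or the sample size.

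**What to change.** 1. In Protocol 9.5, have the reports stratified by group and, within Groups 1 and 3, by dose.
2. For consistency, add 20 mg/kg to Protocol objective 1.2.4 and SAP 2.4 item 4. The PK objective (Protocol 1.3.1 and SAP 2.5 item 1) has the same three-dose list and can be checked at the same time.
3. If Group 3 dosing is already complete, confirm whether the reports were in fact split by dose, and correct the wording.

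The cost is one stratification variable in an existing report and a few wording edits. The drawback is that each Group 3 line rests on about 10 people, so chance differences between the two doses will be common and should not be over-read.

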9.6 Analyses

9.6.1 Analyses of Primary Endpoints

9.6.1.1 Descriptive statistics of EBA₀₋₇ (CFU) for each of the cohorts in Groups 1 and 2 will be reported in a table. Box plots and a plot with four CIs will be created.

9.6.1.2 Descriptive statistics of EBA₀₋₇ (TTD) for each of the cohorts will be reported in a table. Box plots and a plot with six CIs will be created.

9.6.1.3 The relationship between the AUC/MIC and the EBA will be evaluated with linear or nonlinear models, adjusting for other covariates, such as baseline log₁₀ CFU per mL. PK/PD modeling will be performed to evaluate the relationship between drug concentrations and rate or magnitude of bacterial decline. The distributions of PK/PD parameters will be examined first and appropriate transformations will be applied if necessary.

9.6.1.4 Grade 2 or higher AEs will be reported in a tabular form by **cohorts**.

9.6.2 Analyses of Secondary Endpoints

9.6.2.1 INH PK parameters will be estimated using noncompartmental analysis and the descriptive statistics will be reported by NAT2 genotype status (See [section 10.0](#)).

9.6.2.2 The distribution of INH MIC against *M. tuberculosis* isolates with *inhA* mutation, *katG* mutation, or neither of these mutations will be reported.

9.6.2.3 The AUC/MIC that achieves 50% of the mean EBA in Group 2 will be estimated and designated the “Target AUC/MIC”. A Monte Carlo simulation will be performed using the MIC distribution (Group 1), NAT2 genotype distribution (Groups 1 and 2), and distribution of AUC values (Groups 1 and 2) associated with each dose and put to estimate the proportion of participants who have TB with an *inhA* mutation in a population would be expected to achieve the target AUC/MIC with 5, 10, or 15 mg/kg daily. **As exploratory analysis, the same analysis will be performed for Group 3 to determine which proportion of individuals with TB with a *katG* mutation would be expected to achieve the target AUC/MIC with a dose of 15 or 20 mg/kg daily.**

9.6.2.4 The same analysis below will be conducted separately based on \log_{10} CFU and TTD. If the number of phases is the same for every dosing **cohort**:

- **Six bi-exponential models for \log_{10} CFU and four bi-exponential models** will be fit in order to estimate the “early” and “late” phase slopes for each **cohort**. Since this is an INH mono-therapy study, there may be an inflection point at Day 2 after the initiation of INH treatment.

If the number of phases is not the same for every dosing **cohort**:

- **Six linear or nonlinear mixed effect models for \log_{10} CFU and four linear or nonlinear mixed effect models for TTD** will be fit in order to estimate treatment effect for each **cohort**.
- (For \log_{10} CFU only): Another approach will be taken to utilize the area between baseline CFU per mL and the CFU curve (ABBCC) for each participant, as measured using the trapezoidal rule. Since baseline CFU per mL may differ substantially between **groups**, the ABBCC will be expressed as a proportion of the total area under the baseline CFU per mL. The descriptive statistics will be reported **for each cohort**.

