The main reason for this CM is to clarify the target accrual for the study. In addition, the ACTG Web site address has been updated, and the laboratory requirement for CD4+ count testing has been updated to comply with the DAIDS policy on Requirements for DAIDS Funded and/or Sponsored Laboratories in Clinical Trials.

The following are clarifications to Protocol A5312, Version 3.0, 08/21/18, titled "The Early Bactericidal Activity of High-Dose or Standard-Dose Isoniazid among Adult Participants with Isoniazid-Resistant or Drug-Sensitive Tuberculosis." These clarifications will be included in the next version of the A5312 protocol if it is amended at a future date.

1. There were 259 total participants enrolled in A5312 prior to the implementation of Version 3.0; this includes 64 participants who were enrolled in Group 3, Step 1. Under Version 3.0, the target accrual for Group 3, Step 2, is 20 participants. Since some participants who screen for the study will qualify for Step 1 and not for Step 2, it is expected that 20 additional participants will enroll in Group 3, Step 1 only. Thus, the total accrual for the study is 299 participants (259 under Version 2.0, and 40 participants under Version 3.0). Participants in Group 3, Step 2, who discontinue before the day 7 sample collection will be replaced and are not included in the calculation for target accrual. Below is the breakdown of enrollment by group and step:

Group	Step	Actual Accrual prior to Version 3.0	Expected Accrual under Version 3.0	Target Accrual (Actual + Expected)
1	1 only	66		66
	1 + 2	44		44
2	1 only	69		69
	1 + 2	16		16
3	1 only	64	20	84
	1 + 2		20	20
				Total: 299

2. Study Management, Copies of the Protocol: The text has been revised to read:

To request hard copies of the protocol, send a message to [contact] via e-mail. Electronic copies can be downloaded from the ACTG Web site (<https://actgnetwork.org>).

3. Section 4.3, Inclusion Criteria for Step 2, Criterion 4.3.6:

For HIV-positive candidates only: CD4+ count of ≥ 50 cells/mm³, performed within 7 days prior to entry at **any network-approved laboratory that is IQA-certified**.

4. Section 6.3, Instructions for Evaluations. The following language has been added as the first paragraph in this section:

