9.4 Sample Size and Accrual

Primary Objectives:

One of the primary objectives is to estimate the distribution of the EBA_{0-7} (CFU) from each cohort in Group 1 (5, 10, and 15 mg/kg of INH for participants with an *inhA* mutation) and the EBA_{0-7} (CFU) from Group 2 (5 mg/kg of INH for participants without *katG* or *inhA* mutations). **Another primary objective is to estimate the distribution of the EBA_{0-7} (TTP) from each cohort in Group 1, Group 2, and each cohort in Group 3.** The aim is to establish proof-of-concept for the higher doses of INH.

Sample Size:

The planned sample size is 16 participants per treatment **cohort in Group 1 and Group 2**; participants discontinuing before the day 7 sample collection will be replaced. This sample size is similar to that of other recent exploratory EBA studies.

Here is some information about the likely precision of estimates that can be achieved with the planned sample size of 16 participants in this proof-of-concept study. Among participants with DS-TB who were taking 300 mg doses of INH, the estimated mean EBA_{0-5} was $0.21 \log_{10}\text{CFU/mL/day}$ ($n=16$, SE 0.03, between-participant SD 0.12, coefficient of variation [CV] 57%) [41]. We assume the mean EBA_{0-7} (CFU) from Group 1 is approximately half of EBA_{0-7} (CFU) from Group 2. Further assuming constant CV, the table below gives the anticipated precisions (half-widths) of 95% confidence intervals (CIs) around estimates of $\log_{10}\text{CFU/mL/day}$ for any one Group 1 cohort and for the Group 2 cohort, for sample sizes of 10, 16, and 20. Because the MIC distribution may be more variable for Group 1, the table also shows anticipated CI widths for a Group 1 cohort if the CV and SD are larger (114% and 0.120, respectively).

Table 9.4-1: Sample Size per Arm and Expected Half-width of 95% CI for the Hypothesized Mean \log_{10} CFU/mL Decrease per Day with a Range of Estimated CV and SD

Group	Sample Size per Group	Hypothesized Mean \log_{10} CFU/mL/day	CV	SD	Expected Half-width of 95% CI
Any one Group 1 cohort	10	0.105	57%	0.060	0.043
	16	0.105	57%	0.060	0.032
	20	0.105	57%	0.060	0.028
Any one Group 1 cohort	10	0.105	114%	0.120	0.086
	16	0.105	114%	0.120	0.064
	20	0.105	114%	0.120	0.056
Group 2	10	0.210	57%	0.120	0.086
	16	0.210	57%	0.120	0.064
	20	0.210	57%	0.120	0.056

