For Group 1 cohorts, the sample size of 16 is required for a two-sided 95% CI with a precision (half-width) of less than or equal to 0.064 with SDs between 0.060 and 0.120. This means that, for example, if the mean of EBA₀₋₇ (CFU) from the 15 mg/kg of INH for participants with an *inhA* mutation is 0.1 and the SD is 0.12, there is 95% probability that the CI of 0.04 and 0.17 covers the true mean.

Similarly, if the mean of EBA₀₋₇ (CFU) from Group 2 is 0.2 and the SD is 0.12, there is 95% probability that the CI of 0.14 and 0.26 covers the true mean.

This sample size should allow for evaluation of the association between AUC/MIC and EBA₀₋₇, one of the other primary analyses, with high precision, as the data from all experimental dosing cohorts will be pooled for this PK/PD analysis [9, 13, 15, 42].

For Group 3, the sample size of 10 per dosing cohort was selected since the analysis of EBA₀₋₇ (TTP) per dosing cohort will be exploratory. Assuming the SD for Group 3 cohorts will be 6, which is the overall SD of EBA₀₋₁₄ (TTP) from the previous ACTG EBA study (A5307, unpublished), a half-width of a 95% CI is 0.086 with the sample size of 10. This means, for example, if the mean of EBA₀₋₇ (TTP) from a dosing cohort in Group 3 is 13, there is 95% probability that the CI of 9.28 and 16.7 covers the true mean. A possible dosing effect for this group will be examined through visual displays.

Accrual:

During Stage 1, five participants were recruited to each cohort in Group 1. During Stage 2, 11 additional participants will be recruited to each cohort in Group 1, **20 participants in Group 3**, and 16 participants in Group 2 will be recruited. In the final analyses, the data from both stages will be combined. The time to accrual for this study (Stage 1 and 2 combined) is approximately **4 years**.

To maintain desired precision of estimation (primary analyses), participants who discontinue the study prior to the Day 7 evaluations will be replaced. All data from every randomized participant will be stored in the study database, and will be examined for the final analyses.

Participants enrolling to Step 1 only will be considered evaluable if all data that are required are available at screening and/or entry regardless of subsequent known or unknown loss to follow up.

Table 9.4-2: A5312 Accrual Targets

	Resistance Mutation	Participants Completing Step 1 Only ¹	Participants Completing Step 1 and Step 2 ²		Total Participants

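### The attainment proportions for objective 1.3.3 rest on an estimated target AUC/MIC whose sampling error no available document carries forward or reports

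*Protocol*

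**What the plan says.** Objective 1.3.3 asks what proportion of participants with an *inhA* mutation reach, by dose, an AUC/MIC associated with at least half the EBA of standard-dose INH in drug-sensitive TB. Protocol 9.6.2.3 answers it in two steps. First, "The AUC/MIC that achieves 50% of the mean EBA in Group 2 will be estimated and designated the" target. Second, "A Monte Carlo simulation will be performed using the MIC distribution (Group 1), NAT2 genotype distribution (Groups 1 and 2") and the AUC distribution in the same two groups. An exploratory version covers Group 3.

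The curve behind the target is described in 9.6.1.3: the relationship "will be evaluated with linear or nonlinear models, adjusting for other covariates". Section 9.2.1.3 gives the data it uses: "Group 1 for CFU and TTD and Group 3 for TTD only". On size, section 9.4 states "The planned sample size is 16 participants per treatment" cohort, which makes 48 in Group 1 and 16 in Group 2. The table in the December 2019 clarification memo, under "Actual Accrual prior to Version 3.0", shows 44 and 16 for Steps 1 and 2.

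On precision, 9.4 says the sample size should allow the AUC/MIC-EBA association to be evaluated "with high precision, as the data from all experimental dosing cohorts will be pooled for this PK/PD analysis". It gives no figure.

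Protocol 10.3 places the detailed PK/PD plan in the SAP. SAP 4.3.1 and 4.3.2 pass it on to a separate PK analysis plan. The SAP does plan 95% confidence intervals for mean EBA and mean MIC.

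**The concern.** Both ingredients of the target are estimates: the fitted curve, and the Group 2 mean that sets the height at which the curve is read. The inputs listed for the Monte Carlo step describe variation between people in MIC, acetylator status and exposure. Sampling error in the target is not among them. If 9.6.2.3 is followed as written, each dose gets one attainment proportion computed at one value of the target, and a large simulated population will make that proportion look almost exact.

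These proportions are the answer to objective 1.3.3, and Protocol 2.2 says the study will enable an optimised dosing strategy. A reader comparing doses would not see how far a repeat of the same trial could move them.

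**Working it through.** **1. The plan's own precision figure.** Half-width = t(0.975, n−1) × SD/√n. For n = 16, SD 0.12: 2.131 × 0.12/4 = 0.064. For SD 0.06: 0.032. Both match Table 9.4-1, as do the rows for n = 10 and 20 and the 0.053 for n = 22 in section 9.5. These figures cover cohort means only. Nothing comparable is given for the curve or the target.

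**2. Group 2 mean alone, curve treated as known.** Section 9.4 gives mean 0.21 and SD 0.12 (from an EBA over days 0 to 5). Half of 0.21 ± 0.064 runs from 0.073 to 0.137. For an Emax curve, target = EC50 × T/(Emax − T), where T is that threshold. Protocol 2.1 puts half-maximal effect at AUC/MIC of about 60. Emax is an assumption.

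| Emax | EC50 | Target at T = 0.073 | Target at T = 0.137 | Ratio |
|---|---|---|---|---|
| 0.21 | 60 | 60 × 0.073/0.137 = 32 | 60 × 0.137/0.073 = 113 | 3.5 |
| 0.233 | 60 | 60 × 0.073/0.160 = 27 | 60 × 0.137/0.096 = 86 | 3.1 |
| 0.30 | 60 | 60 × 0.073/0.227 = 19 | 60 × 0.137/0.163 = 50 | 2.6 |

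So about 3-fold, before any error in the curve.

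**3. Both sources together, by simulation (2,000 to 3,000 trials per setting).**
- From the documents: *inhA* MIC 0.2 to 1 and susceptible MIC 0.03 to 0.06 mcg/mL; mean EBA 0.105 in Group 1 and 0.21 in Group 2; Group 2 SD 0.12; Group 1 SD 0.06 to 0.12.
- Assumed: Emax or log-linear fit; 40% slow acetylators; AUC per mg/kg of 5.0 (slow) and 2.8 (fast); log-SD of AUC 0.3; log-uniform *inhA* MIC; no error in measured AUC or MIC. The assumed fast/slow ratio, 2.8/5.0 = 0.56, is a little above the 30% to 50% in Protocol 2.1. The fast value is a little below 48.2/15 = 3.2 from the study cited there.
- Calibrating to the two means gives Emax 0.281 and EC50 129, so the true target is 129 × 0.105/(0.281 − 0.105) = 77.
- The plan's SDs are total SDs, so the part explained by exposure (0.0456 across Group 1) is removed. Residual SD = √(0.06² − 0.0456²) = 0.039, and √(0.12² − 0.0456²) = 0.111.

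| Group 1 total SD | Upper/lower 95% limit of the target (n = 44 or 48) |
|---|---|
| 0.06 | 2.8 to 3.1 |
| 0.09 | 3.5 to 4.5 |
| 0.12 | 4.7 to 10 |

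The range within each row reflects n, curve form and whether Group 2 enters the fit. With half-effect near AUC/MIC 60 and total SDs, the ratio is about 3.6 to 4 at SD 0.06. At SD 0.12 it is 15 or more, and in some trials the fitted curve never reaches the threshold, so the target is unbounded.

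**4. Effect on attainment.** Calibrated model, n = 48, Emax fitted to Group 1, target at its lower limit, median and upper limit:

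| Dose | SD 0.06 (target 44, 77, 122) | SD 0.12 (target 30, 79, 203) |
|---|---|---|
| 5 mg/kg | 0.44, 0.15, 0.03 | 0.67, 0.14, 0.00 |
| 10 mg/kg | 0.81, 0.51, 0.25 | 0.94, 0.50, 0.07 |
| 15 mg/kg | 0.95, 0.74, 0.48 | 0.99, 0.73, 0.20 |

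**5. Favourable variants.** With Group 2 SD 0.06 instead of the stated 0.12, the ratio falls to about 1.9 to 3.0. With the threshold essentially known and Group 1 SD 0.06, the curve alone gives 1.57. The Group 2 mean is therefore the larger source at the favourable end.

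**The case against.** The strongest objection is that the governing document is missing. SAP 4.3.2 assigns endpoint 9.2.2.3 to a separate PK analysis plan, and 9.6.2.3 is only an outline. A reader might infer that the plan treats the target as known. The documents do not say so: they say it is estimated, and are silent on its error. That limit stands. It does not remove the gap, because Protocol 10.3 says the detail is in the SAP and the SAP does not contain it.

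Three objections to the size also stand in part.
- A reader might take 4-fold as a floor. It is not: the calibrated model gives about 3-fold at SD 0.06.
- Using 0.06 and 0.12 as residual SDs would count MIC-driven variation twice, since 9.4 introduces the larger SD because MIC may vary more. The figures above treat them as total SDs.
- The planned analysis uses daily counts and adjusts for covariates such as baseline log10 CFU, which could narrow the range. The check used one unadjusted slope per person. The TTD analysis adds up to 20 Group 3 participants and was not simulated.

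Finally, 9.4 claims precision for the association, not for a target read off the curve. A reader might infer that the claim has been shown false for the association; the check does not show that. It shows that the claim has no calculation behind it and cannot be extended to the target. Accrual to Groups 1 and 2 is over and their primary report is dated September 2018, so rewording 9.4 changes no analysis.

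**Conclusion.** The concern holds in this form: the available documents estimate the target from 44 to 48 Group 1 and 16 Group 2 participants, simulate attainment from MIC, NAT2 and AUC alone, and request no interval on the target or on the proportions. Under the stated assumptions the target's 95% sampling range is about 3- to 4-fold at Group 1 SD 0.06 and about 5-fold to 15-fold or more, sometimes unbounded, at SD 0.12. The exact multiple depends on the SD and on the curve, whose form the protocol leaves open. The conclusion does not depend on the larger figures: the Group 2 mean alone gives about 3-fold, and even the favourable calibrated case moves attainment at 10 mg/kg by 0.81 − 0.25 = 56 percentage points. This is a secondary, estimation-only objective with no decision rule, so the harm is a misleading appearance of certainty rather than a wrong test.

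**What to change.** In Protocol 9.6.2.3 and in the PK analysis plan, bootstrap participants within cohort. In each replicate:
1. recompute the Group 2 mean;
2. refit the covariate-adjusted curve;
3. read off the target;
4. re-estimate the MIC, NAT2 and AUC inputs;
5. rerun the attainment simulation.

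Report 95% intervals for the target, allowing an unbounded limit where the fitted curve does not reach the threshold, and for the attainment proportion at each dose. Do the same for the exploratory Group 3 version. If the PK plan already does this, a cross-reference from 9.6.2.3 and the SAP is enough.

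In 9.4, remove the claim made in "one of the other primary analyses, with high precision", or replace it with a simulated expected interval for the AUC/MIC-EBA relationship under the SDs in Table 9.4-1. An interval for a linear correlation would not serve, because the model may be nonlinear.

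The cost is a loop around code that is needed anyway and one edited sentence; no new data or visits. The downside is that the proportions will look less certain.
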